12.5 Physical Examinations

Physical Examination assessments will be listed for all time points.

12.6 Substance Use

Alcohol consumption within 7 days prior to each visit will be listed.

12.7 Pregnancy Test Results

All information related to pregnancy testing (urine and serum based - beta-human chorionic gonadotropin) and contraception status will be listed. This listing will include all pregnancy test results collected during the study.

12.8 Concomitant Medications

Prior medications are defined as any medication where the use was stopped prior to the first administration of the study medication.

Concomitant medications are defined as any medication (other than the study drug) that was used at least once after the first administration of the study medication. Medications that were stopped on the same date as the first study drug administration will be analyzed as concomitant medications. If a clear determination cannot be made (partial medication end dates) the medication will be classified as concomitant.

12.8.1 *Biostatistical Methods*

Concomitant medications will be summarized by ATC class Level 3 and PT. Within each category, the number of subjects who used the medication (count and percentage) will be presented. Subject who used the same medication on multiple occasions will only be counted once in the specific category (PT). PTs will be sorted alphabetically. In addition to the summaries by the coded terms, the number of subjects who used at least one concomitant medication during the study will be presented.

All information that was collected on the Concomitant Medication eCRF as well as the coded WHO-DD terms will be included in the listings.

Prior medications will be listed only.

13. ANTIVIRAL ACTIVITY

Antiviral activity endpoints will be analyzed using the antiviral analysis set. All information will be presented by treatment group, overall by study part (Parts B & C). All antiviral activity data will be listed by cohort and study part.

13.1 Definition of variables

- Maximum reduction of serum HBsAg from Day 1 until Week 16.
 - Serum log₁₀ HBsAg levels by timepoint
 - Serum log₁₀ HBsAg levels < 10000 IU/mL, <1000 IU/mL and < 100 IU/mL by timepoint
- Serum log₁₀ HBsAg Nadir level per subject, summarize as continuous and categories of < 10000 IU/mL, <1000 IU/mL and < 100 IU/mL
- Time to Nadir, Nadir value and Nadir change from baseline value
- Number of subjects with serum HBsAg loss at any timepoint.
- Number of subjects with sustained serum HBsAg loss for ≥ 6 months.
- Number of subjects with anti-HBs seroconversion at any timepoint.
- For HBeAg-positive subjects (Part C only): number of subjects with HBeAg loss and/or anti-HBe seroconversion at any timepoint.

CCI

13.2 Biostatistical methods

All antiviral data collected at scheduled and unscheduled visits will be included in the listings, but only results collected as scheduled visits will be included in the summary tables.

The parameter names that will be used in the outputs will comprise of the test name and the unit of measure, for example, HBsAg (IU/mL). For HBV DNA both IU/mL and copies/mL CCI will be presented. For HBV DNA, undetected and <LOQ will be imputed as 9 U mL. Parameters will be sorted within parameter class (if present) in alphabetical order within the tables and listings.

Summary for serum log₁₀ HBsAg nadir level and time to nadir will be based on all scheduled and un-scheduled post-baseline visits. Measurements will present summary statistics for the results at the baseline and each scheduled post-baseline visit for each of the parameters. In addition, summaries will be presented for the change from baseline of the antiviral measure to that assessed at baseline values at each scheduled post-baseline visit. See section 3.1 for more detail with regards continuous data representation. Categorical summaries (% of subjects) will present counts and percentages for the reported results at baseline and each post-baseline time point. Additionally, HBV DNA CCI will be summarized into TND, <LOQ, and >LOQ categories.

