3.2. Part B/C Endpoints

The primary endpoints are:

- Incidence of AEs
- Clinical assessments including but not limited to laboratory test results

The secondary endpoints are:

- PK parameters of VIR-2218 and possible metabolites (may include, but not limited to plasma: maximum concentration, time to reach maximum concentration, area under the concentration versus time curve [to the last measurable timepoint and to infinity], apparent terminal elimination half-life, clearance, and volume of distribution)
- Maximum reduction of serum HBsAg from Day 1 until Week 16
- Number of subjects with serum HBsAg loss at any timepoint
- Number of subjects with sustained serum HBsAg loss for ≥ 6 months
- Number of subjects with anti-HBs seroconversion at any timepoint
- For HBeAg-positive subjects (Part C only): number of subjects with HBeAg loss and/or anti-HBe seroconversion at any timepoint

CCI

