^c Additional HBsAg monitoring is required for subjects with HBsAg levels with a > 10% decrease from the Day 1 predose level at the Week 16 visit. Visits will occur every 4 weeks starting at Week 20 up to Week 48 or until the HBsAg level returns to ≥ 90% of the Day 1 predose level. For example, if Day 1 predose HBsAg is 560 IU/mL and Week 16 HBsAg is 490 IU/mL, the subject will be followed until HBsAg levels returns to ≥ 504 IU/mL. Additional HBsAg monitoring may be discontinued at the Sponsor’s discretion based on emerging data.

^d A complete medical history will be taken at screening including HBV genotype if available. Any changes should be updated prior to dosing.

^e Evaluation of inclusion criteria related to urine pregnancy testing and urine drug screen.

^f See Section 7.2.1 for assessments to be performed during a full physical examination.

^g Subjects’ alcohol intake will be recorded while on study.

^h Vital signs (blood pressure, pulse rate, respiratory rate, and temperature) should be measured in the supine position after the subject has rested comfortably for approximately 10 minutes. On Day 1, vital signs should be measured within 2 hours predose and 4 hours post-dose. On all other visit days, vital signs are only required to be recorded once during the visit.

ⁱ 12-lead safety ECGs will be recorded on the timepoints listed in Appendix 5 and should be measured in the supine position after the subject has rested comfortably for 10 minutes.

^j WOCBP are required to have pregnancy tests. A serum pregnancy test will be performed at screening and urine pregnancy tests will be performed thereafter. Negative pregnancy test must be confirmed prior to study drug administration.

^k Does not need to be performed if the subject has had a FibroScan in the 6 months prior to screening or liver biopsy in the year prior to screening that confirmed the absence of Metavir F3 fibrosis or F4 cirrhosis.

^l See Section 7.1.3 for viral serology parameters.

^m Clinical laboratory and urinalysis parameters are described in Section 7.2.8.

ⁿ Liver function tests only.

^o Drugs of abuse included in the screen are described in the inclusion/exclusion criteria. Screening results for drugs of abuse must be reviewed prior to dosing.

^p Study drug will be administered via SC injection as described in Section 6.2.4.

^q Blood samples for PK analysis will be collected at the timepoints listed in Appendix 5.

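### HBsAg nadir and time to nadir are taken over follow-up whose length depends on HBsAg itself, so they are not directly comparable across cohorts or with placebo

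*SAP*

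**What the plan says.** **The endpoint.** Protocol 3.2 lists as a secondary endpoint "Maximum reduction of serum HBsAg from Day 1 until Week 16". SAP 2.3.2 and 13.1 repeat it with the same window.

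**The nadir variables.** SAP 13.1 separately lists the log10 HBsAg nadir level (continuous and in categories) and "Time to Nadir, Nadir value and Nadir change from baseline value". None of these has a window.

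**The samples used.** The general rule in SAP 13.2 is that "only results collected as scheduled visits will be included in the summary tables". The nadir is an exception: its summaries for "nadir level and time to nadir will be based on all scheduled and un-scheduled post-baseline visits". That sentence names only level and time. That it also governs nadir change and the nadir categories is an inference, since both are computed from the nadir level.

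**Who is sampled after Week 16.** Protocol Appendix 3, footnote c, requires further monitoring only for "subjects with HBsAg levels with a > 10% decrease from the Day 1 predose level at the Week 16 visit". On timing it says "Visits will occur every 4 weeks starting at Week 20 up to Week 48 or until the HBsAg level returns to ≥ 90" per cent of the Day 1 value. It adds: "Additional HBsAg monitoring may be discontinued at the Sponsor’s discretion based on emerging data".

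The SAP text gives no rule for unequal follow-up and does not say how the nadir summaries relate to the Week 16 maximum reduction.

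**The concern.** A minimum depends on how many samples it is taken over and for how long. Here the HBsAg result at Week 16, and later results, decide both. A subject back within 10% of Day 1 at Week 16 has a nadir time of about 16 weeks at most. A subject still suppressed can have one as late as Week 48. If the share of extended subjects differs between dose cohorts, or between active and placebo, the nadir summaries mix drug effect with length of observation.

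Two consequences follow. A reader may take a longer mean time to nadir as a pharmacological difference when part of it may come from the sampling rule. The report will also carry two similar quantities, maximum reduction to Week 16 and nadir change from baseline, which may differ without explanation.

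Cohort size makes this visible. A basic Part B/C cohort has 4 subjects randomized 3:1, so 3 on VIR-2218. If one of the three has a recorded nadir at Week 40 instead of Week 12, the cohort mean moves by (40 − 12)/3 = 9.3 weeks.

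**Working it through.** **1. The plan's own example.** Appendix 3, footnote c, uses Day 1 = 560 and Week 16 = 490 IU/mL. The fall is 1 − 490/560 = 12.5%, above 10%, so monitoring is extended. The exit level is 0.90 × 560 = 504 IU/mL, as stated. The trigger on the log scale is log10(0.90) = −0.046.

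**2. Sample counts** (Appendix 3, HBsAg row).
- To Week 16: Day 2, Weeks 1 to 8, Week 12, Week 16 = 1 + 8 + 1 + 1 = 11.
- Extension: Weeks 20, 24, 28, 32, 36, 40, 44, 48 = 8.
- Maximum: 11 + 8 = 19 samples over 48 weeks, a window 48/16 = 3 times as long.

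**3. Direction.** The samples to Week 16 are a subset of all samples. So the all-visit minimum is at or below the Week 16 minimum. Its time is either unchanged or later than Week 16. The shift is never negative, but it can be zero.

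**4. Size in extended subjects.** The documents give neither the response shape nor the assay noise, so both are assumed: a mean depth of 1 log10 and noise SD of 0.05 log10 per measurement, simulated with the >10% entry rule and the ≥90% exit rule.

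| Assumed shape | Mean time to nadir, to Week 16 | All visits | Shift (weeks) |
|---|---|---|---|
| Nadir Week 8, rebound by Week 48 | 8.3 | 8.3 | 0 |
| Nadir Week 12, rebound by Week 48 | 12.3 | 12.3 | 0 |
| Plateau Weeks 12–24, then rebound | 14.0 | 18.0 | 4 |
| True nadir at Week 20 | 16.0 | 20.1 | 4 |
| Flat plateau Weeks 12–48 | 14.0 | 30.0 | 16 |

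The plateau rows can be checked by hand, because each plateau sample is equally likely to be the lowest:
- Weeks 12 and 16 average 14.
- Weeks 12, 16, 20 and 24 average 18.
- Weeks 12, 16, …, 48 (10 samples) average 30.

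The mean nadir was deeper by 0 to about 0.2 log10. The largest difference came from the true Week 20 nadir, which a Week 16 limit would miss. Noise of 0.03 or 0.08 log10 gave the same pattern.

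**5. Flat placebo.** With noise SD σ on both the Day 1 and Week 16 values, the chance of extension is Φ(−0.046/(√2·σ)). This is 14% at σ = 0.03 and 34% at σ = 0.08. Most placebo subjects would stop at Week 16. In those extended by noise alone, mean time to nadir goes from 8.6 to 10.3 weeks (σ = 0.03) and from 7.2 to 10.5 weeks (σ = 0.08).

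**The case against.** The case for leaving the SAP alone has real content.

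- **The endpoint is intact.** A reader might infer that the SAP has redefined the protocol endpoint. It has not: maximum reduction to Week 16 remains its own variable, and extra descriptive variables may use another window. This stands.
- **Inflation is not shown.** A reader might infer that time to nadir is inflated in responders, or must lengthen with dose. The documents do not support that. The shift is zero when HBsAg is lowest early and then rebounds. A true nadir after Week 16 is correctly recorded as late. The 90% exit rule usually stops sampling only after a responder's nadir has passed. Whether a dose gradient appears depends on response shapes that the documents do not give. This stands.
- **Extended is not the same as responder.** Entry rests on one Week 16 value. Noise can extend a placebo subject, and an early responder who has recovered by Week 16 is not extended. This stands.
- **Large chance figures need a special shape.** On a perfectly flat plateau from Week 8 to Week 48, 8 of 11 plateau samples (73%) fall after Week 16. With the last dose at Week 4, that is one end of the range and not a typical case.
- **A Week 16 limit used alone would censor late nadirs.** This stands and shapes the fix.
- **Other outputs help.** HBsAg is summarised by visit and all antiviral data are listed, so individual courses can be seen. The list of tables is redacted, so a Week 16 nadir table may exist there. Even so, the SAP text does not define one.

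None of this removes the core point: the windows are unequal, the outcome sets them, and the SAP text neither says so nor handles it.

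**Conclusion.** The point holds in a limited form. HBsAg nadir level and time to nadir, and by inference nadir change and the nadir categories, are computed over windows that differ between subjects and depend on the outcome: 11 scheduled samples over 16 weeks, or up to 19 over 48 weeks. They are not directly comparable across dose cohorts or with placebo. Nadir change may equal or exceed the Week 16 maximum reduction, and the SAP does not explain the relation.

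Under the assumed shapes and noise, mean time to nadir in extended subjects shifts by 0 to about 16 weeks. The documents do not say which shape applies, so the size is a range and not a prediction. No hypothesis test or sample size calculation is affected, because SAP 3.3 plans none and SAP 2.4 has none. This is a cheap improvement to interpretability.

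**What to change.** In SAP 13.2:

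1. Summarise nadir level, nadir categories, nadir change and time to nadir using samples through each subject's Week 16 visit. Make this the between-cohort and placebo comparison tied to the endpoint. Identify the visit by its nominal label and not by a date window, so that it agrees with SAP 3.1, which does not exclude assessments made outside protocol windows.
2. Keep the all-visit nadir and time to nadir as a separate summary, labelled as such and showing each subject's last sampling week, so that true late nadirs are not censored.
3. Apply one rule on unscheduled values to both the Week 16 nadir and the Week 16 maximum reduction. At present the nadir has an explicit exception, and the text does not say whether the maximum reduction shares it.

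The cost is a few sentences in the SAP, a visit filter in programming and one extra table. No data are lost and nothing changes in trial conduct.

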9.7. Antiviral Activity Analysis

For Part B/C, selected data relating to the antiviral activity of VIR2218, such as HBsAg, HBeAg, CCI [REDACTED], anti-HBs, anti-HBe, CCI [REDACTED], and HBV DNA levels, will be summarized (n, mean, SD, median, Q1, Q3, minimum, and maximum) by cohort and study visit along with corresponding change from baseline. Summaries (number and percentage of subjects) of HBsAg loss, anti-HBs seroconversion, HBeAg loss, and anti-HBe seroconversion will be provided by cohort and study visit.

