2. PROJECT OVERVIEW

2.1 Study Design

Part A to C:

[figure not shown]
This is a randomized, double-blind, placebo-controlled study of VIR-2218 administered subcutaneously to healthy adult subjects and non-cirrhotic adult subjects with chronic hepatitis B virus (HBV) infection who are on nucleos(t)ide reverse transcriptase inhibitor (NRTI) therapy. The study is designed to evaluate the safety, tolerability, Pharmacokinetic (PK), and antiviral activity of VIR-2218. Part A is planned to be conducted at 1 clinical investigative site; Parts B and C are planned to be conducted at multiple clinical investigative sites in the Asia-Pacific region. The study designs for Part A, phase 1 single ascending dose (SAD) and Part B/C, phase 2 multiple ascending dose (MAD) are presented in Figure 1 and Figure 2, respectively.

Figure 1: **SAD Study Design for Part A**

^aSubject discharge will occur after all assessments are completed on Day 2.

Figure 2: **MAD Study Design for Part B/C**

^aAdditional Hepatitis B Surface Antigen (HBsAg) monitoring is required for subjects with HBsAg levels with a > 10% decrease from the Day 1 predose level at the Week 16 visit. Visits will occur every 4 weeks starting at Week 20 up to Week 48 or until the HBsAg level returns to > 90% of the Day 1 predose level. Additional HBsAg monitoring may be discontinued at the Sponsor's discretion based on emerging data.

Part A Single Ascending Dose Phase in Healthy Adult Subjects

Healthy adult subjects will be enrolled in 1 of 4 planned ascending dose cohorts. At the start of each cohort, 2 sentinel subjects will be randomized 1:1 to VIR 2218 or placebo. These subjects will be dosed concurrently and monitored for 24 hours; if the investigator has no safety concerns, the remainder of the subjects in the same cohort will be dosed. Vital signs, symptom-directed physical examination(s), and AEs will be reviewed by the investigator prior to dosing any additional subjects. The remaining subjects will be randomized 5:1 to receive a single dose of VIR 2218 or placebo.

Subject screening will occur no more than 4 weeks prior to the Day 1 visit. Eligible subjects will be confined to the clinical investigative site on Day -1 to determine continued eligibility and for predose assessments. Subjects in each cohort will be randomized to receive VIR-

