5. SUBJECT DISPOSITION AND ANALYSIS SETS

Outcomes will be summarized by treatment and overall, by study part. All outcomes will be listed by study part and cohort.

5.1.1 *Subject Disposition*

Subject disposition will be summarized using counts and percentages and will be based on the All Randomized Analysis Set for Part A to C. The number and percentage of subjects who completed treatment, completed the study per protocol (this means 16 week or 48 week follow up for the relevant parts), along with primary reason for treatment discontinuation and early termination will be summarized by treatment arm.

All disposition information collected will be listed together with the date that the subject provided informed consent and the date and time of study drug administration.

5.1.2 *Analysis Sets*

The number of subjects included in each of the defined analysis sets will be summarized using counts and percentages and will be based on the all randomized set.

In addition, the inclusion of each subject into/from each of the defined analysis sets will be listed by the all screened analysis set.

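### By-visit HBsAg summaries at Weeks 20–48 would describe only subjects still suppressed at every earlier visit from Week 16, so they should not be read as durability

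*SAP*

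**What the plan says.** **Who is measured after Week 16.** All Part B/C subjects are followed to Week 16. Under protocol Appendix 3, footnote c (also section 4.1.2), further "monitoring is required for subjects with HBsAg levels with a > 10% decrease from the Day 1 predose level at the Week 16 visit". Visits are then 4-weekly from Week 20 to Week 48, or "until the HBsAg level returns to ≥ 90% of the Day 1 predose level". A second way out does not depend on the subject's own value: "Additional HBsAg monitoring may be discontinued at the Sponsor"'s discretion. SAP 2.1 words the exit line differently: "until the HBsAg level returns to > 90% of the Day 1 predose level".

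**What is summarized.** Protocol 9.7 says that HBsAg and the other markers "will be summarized (n, mean, SD, median, Q1, Q3, minimum, and maximum) by cohort and study visit along with corresponding change from baseline". SAP 13.2 says that "summaries will be presented for the change from baseline of the antiviral measure to that assessed at baseline values at each scheduled post-baseline visit", and also: "Categorical summaries (% of subjects) will present counts and percentages for the reported results at baseline and each post-baseline time point". Neither stops at Week 16, and Appendix 3 schedules HBsAg at Week 20, Week 24 and every 28 days after that. SAP 13.1, however, nests the by-timepoint HBsAg levels, both the log10 values and the IU/mL categories, under the endpoint of maximum reduction to Week 16. The intended span is therefore not certain.

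**How absent subjects are treated.** SAP 3.1 bases percentages on subjects with non-missing data. SAP 3.2 treats change from baseline as missing when there is no result. SAP 14 imputes nothing for missing values.

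**Disposition.** SAP 5.1.1 counts subjects who "completed the study per protocol (this means 16 week or 48 week follow up for the relevant parts").

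**The concern.** After Week 16, whether a subject is measured depends on the variable being summarized. Subjects whose antigen stayed near Day 1 never enter the extension, and those whose antigen comes back leave it. Those who remain are the more suppressed ones. A late-visit mean can stay low, or even fall, while the dosed group is returning to baseline.

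The displayed n shows that subjects are absent but not why. Never entering, returning to 90%, loss to follow-up and a Sponsor stop look the same. A CSR or manuscript reader would naturally take the Week 24 to Week 48 columns as persistence of effect, and would compare them across doses and with placebo. None of those readings is safe.

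**Working it through.** **1. The protocol's own figure.** Appendix 3, footnote c gives Day 1 = 560 and Week 16 = 490 IU/mL. 490/560 = 0.875, a 12.5% decrease, so the subject enters. The exit line is 0.90 × 560 = 504 IU/mL, as stated. On the log scale the line is log10(0.9) = −0.0458.

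**2. The observation rule.** Let y(t) be the observed log10 change at week t. There are 8 possible extension visits (20, 24, …, 48). Leaving Sponsor stops and ordinary loss aside, a subject has a value at week t only if y(s) < −0.0458 at s = 16, 20, …, t−4. The first value on or above the line is tabulated, and the subject then disappears. The SAP mean therefore estimates E[y(t) | y(16), …, y(t−4) all < −0.0458], not E[y(t)].

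**3. A three-subject active arm** (the planned size: 4 per cohort, 3:1). Assumed fractions of Day 1: A is 0.95 throughout. B is 0.75 at Week 20, 0.93 at Week 28, 0.97 at Week 32 and 1.0 from Week 36. C is 0.12, 0.20 and 0.30 at Weeks 20, 32 and 48. A never enters, and B exits after Week 28.

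| Week | Tabulated mean (n) | All three |
|---|---|---|
| 20 | −0.523 (2) | −0.356 |
| 32 | −0.699 (1) | −0.245 |
| 48 | −0.523 (1) | −0.182 |

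Week 48, all three: [log10(0.95) + log10(1.0) + log10(0.30)]/3 = (−0.022 + 0 − 0.523)/3 = −0.182. The share below half of Day 1 reads 1/1 instead of 1/3.

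**4. Simulation, 200,000 subjects per scenario.** The documents give no decline, return rate or assay SD, so every input here is an assumption: linear log10 return, capped at baseline, with assay SD 0.05 on baseline and each later value.

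| Week 16 decline (SD), mean return per week | Still observed at Week 48 | Tabulated mean | All-dosed mean |
|---|---|---|---|
| 1.5 (0.3), 0.005 | about 100% | −1.34 | −1.34 |
| 1.0 (0.4), 0.01 | 91% | −0.74 | −0.68 |
| 1.0 (0.4), 0.03 | 61% | −0.44 | −0.27 |
| 0.5 (0.4), 0.02 | 44% | −0.33 | −0.14 |

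A wider grid used decline 0.7–1.2, SD 0.4–0.5, return 0.02–0.04 and between-subject CV 0–100%. The tabulated mean lies below the all-dosed mean by 0.004–0.09 log10 at Week 24, 0.02–0.21 at Week 36 and 0.04–0.29 at Week 48. In its middle scenario (0.95, SD 0.5, 0.03, CV 50%), 58% have a Week 48 value and the gap is 0.20. Of those with a value, 88% are below 90% of Day 1. Of all dosed, with non-entrants and leavers counted as returned, 52% are.

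Slower return shrinks the gap: at 0.005–0.015 per week with decline 1.2–1.5 it is about 0.001–0.07 at Week 48. With no return and nobody failing entry it is 0.000.

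**5. Comparisons.** Take two dose groups alike except for return of 0.02 versus 0.04 per week (CV 50%). Their Week 48 means differ by 0.12–0.24 as tabulated and by 0.16–0.35 in all dosed. For placebo with no true change and assay SD 0.03–0.10, 14–37% enter by chance. At assay SD 0.05–0.10 the tabulated Week 24 mean is −0.06 to −0.11 against a true 0.

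**The case against.** **No endpoint depends on these columns.** This stands. Maximum reduction ends at Week 16, HBsAg loss and sustained loss are subject counts, and SAP 3.3 plans no testing. A reader might infer that the trial's antiviral endpoints are biased; the documents do not support that.

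**Other post-Week-16 information exists.** This stands too. SAP 13.2 bases nadir and time to nadir on all post-baseline visits, and every value is listed. It would be wrong to call the by-visit columns the only view of late HBsAg. But nadir does not describe persistence, and listings are not what gets quoted.

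**A return display may be blacked out.** Text is redacted after the Part B/C objectives and endpoints in both documents, in SAP 13.1, in the interim outputs and in the table list. So one cannot say that such a display is missing. If it exists, only its denominator needs checking.

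**The disposition wording is adequate.** Largely so. The protocol itself ends follow-up on return to 90%, so a subject leaving that way at Weeks 20–44 can be read as completing per protocol. A reader might infer that such subjects have no category; the text is loose rather than empty.

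**The bias is small beside the noise.** In the middle scenario the gap is 0.12 at Week 36 and 0.20 at Week 48, against standard errors of about 0.26 and 0.22 for a complete three-subject mean. That is fair for a single cell. The bias is nevertheless systematic, and floater subjects would reduce the noise but not the bias.

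**A footnote would do.** It would prevent much of the misreading, and the fix includes it as one choice. It would not give the all-subject figure.

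**Conclusion.** The point holds, as a minor one. If SAP 13.2 is applied to all scheduled visits, the Week 20–48 HBsAg means and percentages are conditional on continued suppression. They overstate durability to the extent that subjects fail entry or exit, and late placebo columns consist of subjects selected by assay noise. The direction follows from the documents' own rules.

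The size does not. Under the assumptions above, the Week 48 gap runs from about 0 with no return, or with slow return (0.005–0.01 log10 per week) after a large decline, to about 0.2–0.3 log10 at the upper end with return of 0.03–0.04. A reader might take the larger figures as what this trial will show; nothing in the documents fixes where in that range it falls.

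The difference between > 90% (SAP) and ≥ 90% (protocol) is real but matters only at exactly 90%, which is 504 IU/mL in the protocol's example.

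**What to change.** In SAP 13.2, with a matching exception to the SAP 3.1 denominator:

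1. For Weeks 20–48, report the number and percentage of all Antiviral Analysis Set subjects in each dose group still below 90% of Day 1. Count non-entrants and rule-based leavers as returned. Show subjects otherwise missing, or stopped by the Sponsor, separately as unknown.
2. State whether the by-visit HBsAg means and categories end at Week 16. If they continue, label Weeks 20–48 as observed cases in a subset selected on HBsAg, not for comparison across doses or with placebo.
3. Reconcile the exit line between SAP 2.1 and the protocol, so that exit and the counted event share one definition.
4. In SAP 5.1.1, state that rule-based leavers count as completers, and show them separately from other exits.

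A descriptive time-to-return summary is optional; with about three active subjects per planned cohort it adds little.

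**Cost.** SAP wording and modest programming on HBsAg values already collected; no new visits or samples. Cells will be very small, and one noisy value on or above the line counts as returned. With no effect, about 8–15% of placebo subjects would still count as below the line at Week 24 (assay SD 0.05–0.10), a noise floor to state with the table. Late figures will look less favourable.
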